1.1 Synopsis

Protocol Title: A Randomized, Multicenter, Double-Blind, Placebo-Controlled Phase 2 Study to Evaluate the Safety and Efficacy of HMI-115 in Women with Moderate to Severe

Endometriosis-Associated Pain Over a 12-Week Treatment Period

Sponsor Protocol No.: HMI-115EM201

Study Phase: Phase 2

Sponsor: Hope Medicine (Nanjing) Co. Ltd

Rationale:

A First-in-Human (FiH) study with HMI-115 has already established the safety and tolerability of HMI-115 when administered subcutaneously in post-menopausal women aged between 45 to 65 years in single doses up to 240 mg and multiple doses up to 90 mg once every two weeks (Q2W) for 6 weeks. This study aims to evaluate the safety and efficacy of HMI-115 versus a placebo in pre-menopausal women aged 18 to 49 years diagnosed with moderate to severe endometriosis associated pain. The study will determine the safety and efficacy of HMI-115 at 60 mg Q2W, 120 mg Q2W, and 240 mg Q2W.

Objectives and Endpoints:

Objectives	Endpoints					
Primary	Primary					
To study the efficacy of HMI-115	Change in dysmenorrhea (DYS) measured by Numer					
for 12 weeks compared with	Rating Scale (NRS) from Baseline to Week 12					
placebo in the management of						
endometriosis-associated pain						
Secondary	Secondary					
To study the safety, tolerability, and	Efficacy					
persistence of efficacy of HMI-115	1. Change in DYS measured by NRS from Baseline to					
compared with placebo	Week 24					
	2. Change in non-menstrual pelvic pain (NMPP)					
	measured by NRS from Baseline to Week 12 and 24					
	3. Change in dyspareunia (DYSP) measured by NRS					
	from Baseline to Week 12 and 24					

Objectives	Endpoints					
	4. Change from Baseline (CFB) in the monthly mean					
	Endometriosis Daily Impact Pain Scale for DYS,					
	NMPP and DYSP at Week 12 and 24					
	5. CFB by visit in permitted rescue medication use					
	6. Change in menstrual period heaviness (bleeding)					
	from Baseline by visit					
	Safety and tolerability					
	1. Adverse events (AEs)					
	2. CFB by visit in vital signs (blood pressure [BP],					
	pulse, body temperature, and respiratory rate [RR])					
	3. CFB by visit in physical examinations					
	4. Number and ratio of participants used concomitant					
	medication					
	5. CFB by visit in twelve-lead electrocardiogram					
	(ECG)					
	6. CFB by visit in clinical laboratory tests					
	(hematology, coagulation, clinical chemistry,					
	urinalysis, hormones and CA-125)					
	7. CFB in Bone mineral density by Dual energy X-ray					
	absorptiometry (DXA) scan after 12 weeks'					
	treatment (at EOT visit)					
	8. CFB in transvaginal ultrasound (TVU) index					
	(including number and size of ovarian cyst,					
	thickness of endometrium) after 12 weeks' reatment					
	(at EOT visit)					
Exploratory	Other patient-reported outcomes:					
To explore the effect of HMI-115	1. Quality of Life assessment with health-related					
on Quality of Life,	quality of life questionnaire (HRQoL)					
pharmacokinetics (PK), PK-PD	(Endometriosis Health Profile-5 [EHP-5])					
relationship and immunogenicity	2. Response to Patient Global Impression of Change					
	(PGIC)					
	(2 525)					
	PK					
	1. C_{max} , C_{min} , t_{max} , $AUC_{(0-tau)}$, $t_{1/2}$ following last dose					

Objectives	Endpoints
	2. Accumulation ratio (AR) for both C _{max} and AUC
	PK-PD
	Relationship between HMI-115 plasma
	concentration/exposure and pelvic pain score
	measured by NRS (cyclic = DYS,
	non-cyclic = NMPP+DYSP, and average)/side
	effects
	Immunogenicity:
	Anti-drug antibody (ADA)

Overall Design: This is a Phase 2, multicenter, double-blind, placebo-controlled, randomized study to assess the safety and efficacy of HMI-115 subcutaneously administered monoclonal antibody versus placebo in pre-menopausal women with moderate to severe endometriosis-associated pain. The study will comprise of three periods (refer to Figure 1-1):

- 1) A **Screening Period** of up to 75 days prior to first dose:
 - Screening Visit 1
 - Screening Visit 2 (at least 35 days before V3 to ensure at least 5 weeks baseline pain score obtained before randomization)
- 2) A **Treatment Period** (12 weeks). Subjects will be given subcutaneous (s.c.) injections Q2W in the study.
- 3) A **Follow-up Period** of 12 weeks

Number of Subjects:

152 eligible subjects will be randomly assigned to HMI-115 or placebo and 136 evaluable subjects for an estimated total of 34 evaluable subjects per treatment group.

Intervention Groups and Duration:

Eligible subjects will be randomized into four arms: placebo, 60 mg, 120 mg, and 240 mg HMI-115 in a 1:1:1:1 ratio with 38 subjects/arm.

Blood samples will be collected to determine PK profile from Day 1 to Day 169. A full PK sampling strategy will be followed for a subgroup of 10 subjects per arm (refer to Table 1-2). Sparse sampling will be obtained from the rest of the subjects (refer to Table 1-3). Intensive and

sparse PK blood sampling will be performed at timepoints specified in Table 2 and Table 3. Plasma concentrations of HMI-115 will be determined using a validated enzyme-linked immunosorbent assay (ELISA) method. PK parameters will be assessed as described in Section 9.4.9.

[figure not shown]
An e-Diary will be dispensed, and training will be provided to subjects at Visit 2 on how to record endometriosis associated pain, uterine bleeding, and analgesic medication use for endometriosis associated pain on a daily basis. Study related examinations, laboratory assessments and pregnancy testing will be performed according to the schedule of activities (SoA) throughout the study (refer to Table 1-1).

Data Monitoring Committee (DMC) will be used for this study.

Version 6.0 12 of 138 April 11,2024

1.2 Schema

Figure 1–1: Study Design for Part 1 of the Study

1.3 Schedule of Activities (SoA)

Table 1-1 SoA for the study

Procedure	Up to 75 days	ng Period prior to the first ose		Treatment Period EOT ^{4*}						Follow- up Period ^{5*}
Date	Screening Visit	Screening Visit 22	Week 1	Week 3 (Day 15	Week 5 (Day 29	Week 7 (Day 43	Week 9 (Day 57	Week 11 (Day 71	Week 13 (Day 85	Week 25 (Day 169
ACCOUNT OF THE PROPERTY OF THE	Up to 14 days prior to V2	At least 35 days prior to V3	(Day 1) ³	±3)	±3)	±3)	±3)	±3)	±2/4)	±7)
Visit (V)	V1	V2	V3	V4	V5	V6	V7	V8	V9	V10
Informed consent	X									
Inclusion and exclusion criteria	X	x	X							
Demographics	X									
Medical history, current medical conditions	X									
Prior medications	X		3							
Height (cm) and weight (kg) ⁶	X		X		X		X		X	X
BMI (kg/m²)	X						08			
CPSSS assessment	X								X	
Randomization			X							
IMP administration and observe x 1 hour ⁷			X	X	X	X	X	X		
Urine drug screen ⁸	X									
Pregnancy test ⁹	X		X		X		X		X	X
Mammogram ¹⁰		X	5				2,	5		
Cervical cytology ¹¹		X								
DXA scan ¹²		X							X ¹³	
Sellar MRI with contrast ¹²		X					58 578			
TVU ¹⁴		X							X	

Version 6.0 14 of 138 April 11,2024

Procedure	Up to 75 days	ng Period prior to the first ose	Treatment Period EOT ^{4*}					Follow- up Period ^{5*}		
Date	Screening Visit 11 Up to 14 days	Screening Visit 2 ² At least 35 days	Week 1 (Day 1) ³	Week 3 (Day 15	Week 5 (Day 29	Week 7 (Day 43	Week 9 (Day 57	Week 11 (Day 71	Week 13 (Day 85	Week 25 (Day 169
	prior to V2	prior to V3		±3)	±3)	±3)	±3)	±3)	±2/4)	±7)
Visit (V)	V1	V2	V3	V4	V5	V6	V7	V8	V9	V10
Viral Serology ¹⁵	X									
Hematology, clinical chemistry, coagulation and urinalysis ¹⁶	Х		X		X		X		X	
FT3, FT4, TSH, GH and CA 125 ¹⁶	X		X		X		X		X	X
Bone biomarkers (CTX, P1NP, BSAP) ¹⁶			Х						X	
Sex hormone: PRL, LH, FSH, estradiol, progesterone, testosterone, DHEAS ¹⁶	,	x	х		X ¹⁷		X ¹⁷		X ¹⁷	X ¹⁷
eGFR ¹⁸	X								X	
12-lead ECG ¹⁹	X	X	X	X	X	X	X	X	X	X
Vital signs ²⁰	X	X	X	X	X	X	X	X	X	X
Complete physical examination ²¹	X								X	X
Brief physical examination		X	X	X	X	X	X	X		
Pelvic examination ²²	X								X	
e-Diary ²³		X	X ²⁴	X ²⁴	X ²⁴	X ²⁴	X ²⁴	X ²⁴	X ²⁴	X ²⁴
Rescue medication prescription ²⁵		X	X	X	X	X	X	X	X	
AE monitoring	X	X	X	X	X	X	X	X	X	X
Injection site reaction ²⁶			X	X	X	X	X	X	X	
Concomitant medications	X	X	X	X	X	X	X	X	X	X

Version 6.0 15 of 138 April 11,2024

Procedure	Up to 75 days	ng Period prior to the first ose	Treatment Period EOT ^{4*}					Follow- up Period ^{5*}		
Date	Screening Visit	Screening Visit 22	Week 1	Week 3 (Day 15 ±3)	Week 5 (Day 29 ±3)		Week 9 (Day 57 ±3)	Week 11 (Day 71 ±3)	Week 13 (Day 85 ±2/4)	Week 25
	Up to 14 days prior to V2	At least 35 days prior to V3	(Day 1) ³							(Day 169 ±7)
Visit (V)	V1	V2	V3	V4	V5	V6	V7	V8	V9	V10
PGIC			2		X		X	2	X	X
EHP-5			X		X		X		X	X
ADA sampling ²⁷			X	X	X		X		X	X
PK sampling ²⁸			X	X	X		X	X	X	X

Abbreviation: ADA = anti-drug antibody; AE = adverse event; anti-HAV = hepatitis A virus antibody; anti-HIV = human immunodeficiency virus antibodies; ASCUS = atypical squamous cells of undetermined significance; BMI = body mass index; BSAP = bone specific alkaline phosphatase; CA-125 = cancer antigen-125; CPSSS= Composite pelvic signs and symptoms score; CTX = C-terminal telopeptide of type 1 collagen; DXA = dual energy X-ray absorptiometry; DHEAS = Dehydroepiandrosterone-sulfate; ECG = electrocardiogram; e-Diary: Electronic Diary, EHP-5 = Endometriosis Health Profile-5; EOT = end of treatment; FSH = follicle-stimulating hormone; FT3= Free triiodothyronine; FT4= Free thyroxine; eGFR = estimated glomerular filtration rate; GH=growth hormone; HBsAg = hepatitis B virus surface antigen; HBcAb = Hepatitis B core antibody; HCV = hepatitis C virus; LH = luteinizing hormone; IMP = investigational medicinal product; MRI = magnetic resonance imaging; P1NP = procollagen type 1N-terminal propertied; PGIC = Patient Global Impression of Change; PK = Pharmacokinetics; PRL = Prolactin; PVC = Premature ventricular contractions; Q2W = once every 2 weeks; QTcF = QT interval corrected for heart rate using Fridericia's correction formula; RNA = ribonucleic acid; V = Visit; TSH = thyroid stimulating hormone; TVU = transvaginal ultrasound.

- The time interval between Screening Visit 1 and Screening Visit 2 is no longer than 14 days. Specific procedures listed for Visit 1 could be scheduled during this period.
- 2. At Screening Visit 2, e-Diary will be dispensed. The time interval between Visit 2 and Visit 3 will at least cover a 35-day baseline period.
- 3. Day 1 should start from the menses cycle days 1 to 5. Data obtained from Day 1 will be utilized as baseline for analysis (except for e-Diary data).
- 4. The EOT Visit should be 14 days from the last dose of IMP (Visit 8). The time window of EOT visit is dependent on the schedule of the PK subgroup (intensive PK, ±2 days, sparse PK, ±4 days). The arrangement for TVU, pelvic examination or lab tests could be based on menses cycle.
- 5. Refer to Section 7.1 and 7.2 for the follow-up requirement for subjects who discontinue from IMP or withdraw from the study.
- Height at Screening Visit 1 only.
- 7. IMP will be administered Q2W after collecting all testing/examination data at each visit (refer to #20 for additional vital signs at Visit 3). Subjects will be monitored for 1 hour at the site after dosing.
- Urine drug screen includes amphetamine, barbiturates (except for sites in China), benzodiazepines, tetrahydrocannabinol, cocaine, methadone, methamphetamine, opiates, phencyclidine, and tricyclic antidepressants (except for sites in China).
- 9. Serum pregnancy test at Visit 1 only, and urine pregnancy test at Visits 3, 5, 7, 9 and 10. Negative result must be obtained prior to randomization at Visit 3.
- 10. Mammogram for females aged 40 and over only (can be performed at any time during screening period), unless mammography or MRI were performed with normal results within 12 months prior to randomization.

Version 6.0 16 of 138 April 11,2024

- 11. Cervical cytology can be assessed at any time during the Screening period. (Virgins may be exempted per the investigator's discretion)
- 12. DXA scan and Sellar MRI can be assessed at any time during the Screening period. Only subjects who have greater chances of enrollment into the study will undergo DXA scan and Sellar MRI. For subjects who are eligible for randomization, the Screening DXA data will be used as baseline.
- 13. Subjects who discontinue from IMP prior to week 11 or become pregnant during the study does not require a DXA scan. For more details, including subjects who needs further DXA scan after EOT visit, refer to Section 8.2.7.
- 14. TVU should be performed during the early proliferative phase of the subject's menstrual cycle (approximately days 4 through 8). In some circumstances, transrectal or transabdominal ultrasound is allowed per the investigator's discretion.
- 15. Viral serology tests include anti-HAV, HBsAg, HBcAb, anti-HCV, HCV RNA (for positive or equivocal anti-HCV), and HIV antigen/anti-HIV (1+2).
- 16. Clinical laboratory tests are listed in Section 10.2. Samples of sex hormones (PRL, LH, FSH, estradiol, progesterone, testosterone, DHEAS) will be collected at the menses cycle days 1 to 5, and subjects should not take any opioids 2 days prior to blood sampling of PRL.
- 17. Blood samples of sex hormones (PRL, LH, FSH, estradiol, progesterone, testosterone, DHEAS) could be taken on a separate day from the scheduled Visit Day to meet the menses cycle days 1 to 5.
- 18. eGFR will be calculated using the Chronic Kidney Disease Epidemiology Collaboration (CKD EPI) formula.
- 19. 12-ECG can be tested at any time apart from the specified timepoints if the subject feels uncomfortable. If QTc prolongation is found, including repeating PVCs confirmed by additional ECG examination at least 30 minutes apart, or QTcF >500 ms, or increase in QTcF interval >60 ms compared to baseline in the absence of possible causes other than the IMP, drug can be temporarily stopped to investigate the reason. See Section 7.1 for more details.
- 20. Vital signs include blood pressure, tympanic body temperature, pulse, and respiratory rate. Vital signs of subjects will be observed 1 hour after IMP administration on Day 1 and pre-dose at each visit.
- 21. Physical examination: for detailed information, refer to section 8.2.1.
- 22. Pelvic examination: for detailed information, refer to section 8.2.3 and 10.9.
- 23. e-Diary training will be provided at Visit 2, and e-Diary will be dispensed to record endometriosis associated pain (including NRS and scales for DYS, NMPP and DYSP), uterine bleeding, and rescue medication use for endometriosis associated pain on a daily basis from Visit 2 and at approximately the same time every day (morning preferred). Must be completed in the morning prior to arrival at the study site for study visits.
- 24. e-Diary entries compliance will be assessed and additional training will be provided to subjects who have missed data entry.
- 25. Rescue medication and education will be provided to subjects from Visit 2 for rescue use if needed for endometriosis associated pain throughout the study. Refer to table 6-3 for protocol allowed rescue medication.
- 26. All reported AEs to be checked for injection site reaction.
- 27. In addition to the listed sampling time, ADA will also be collected at week 17, together with PK sampling (not required for those who discontinued from IMP or withdraw from study).
- 28. Intensive and sparse PK blood sampling will be performed at timepoints specified in Table 1-2 and Table 1-3.

Note: Blood draws should be performed before vital signs, ECG recordings and physical examinations at visits (can be adjusted according to the condition of the site).

A certified central laboratory will be utilized to process and provide results for all blood tests.

DXA will be analyzed/evaluated centrally by an experienced and qualified imaging vendor.

Procedures that allowed to be repeated during screening period are listed in section 10

Version 6.0 17 of 138 April 11,2024

Table 1-2 Intensive PK Subset (N=10 per arm)

WEEK STUDY DAY		TIME (in r	elation to dosing)	TIME WINDOW
		hour	day	
Week 1	Day 1(first dose)	Pre-dose	Pre-dose	
Week 1	Day 3	+48 h (post-first dose)	+2 day (post-first dose)	+/-2 h
Week 1	Day 5	+96 h (post-first dose)	+4 day (post-first dose)	+/-2 h
Week 1	Day 7	+144 h (post-first dose)	+6 day (post-first dose)	+/-6 h
Week 2	Day 11	+240 h (post-first dose)	+10 day (post-first dose)	+/-12 h
Week 3	Day 15±3	Pre-dose	Pre-dose	Within 2 h before dosing
Week 5	Day 29±3	Pre-dose	Pre-dose	Within 2 h before dosing
Week 9	Day 57±3	Pre-dose	Pre-dose	Within 2 h before dosing
Week 11	Day 71±3(last dose)	Pre-dose	Pre-dose	Within 2 h before dosing
Week 11	Day 73	+48 h (Post-last dose)	+2 day (Post-last dose)	+/-2 h
Week 11	Day 75	+96 h (Post-last dose)	+4 day (Post-last dose)	+/-2 h
Week 11	Day 77	+144 h (Post-last dose)	+6 day (Post-last dose)	+/-6 h
Week 12	Day 81	+240 h (Post-last dose)	+10 day (Post-last dose)	+/-1 day
Week 13	Day 85	+336 h (Post-last dose)	+14 day (Post-last dose)	+/-2 days
Week 17	Day 113	+ 1008 h (Post-last dose)	+42 day (Post-last dose)	+/-7 days
Week 19	Day 127	+1344 h (Post-last dose)	+56 day (Post-last dose)	+/-7 days
Week 21	Day 141	+ 1680 h (Post-last dose)	+70 day (Post-last dose)	+/-7 days
Week 25	Day 169	+ 2352 h (Post-last dose)	+98 day (Post-last dose)	+/-7 days

Version 6.0 18 of 138 April 11,2024

Table 1-3 Sparse PK Sampling

WEEK	STUDY DAY	TIME (in relation to dosing)		TIME WINDOW
		hour day		
Week 1	Day 1(first dose)	Pre-dose	Pre-dose	
Week 1	Day 7	+144 h (post-first dose)	+6 (post-first dose)	+/-2 days
Week 3	Day 15±3	Pre-dose	Pre-dose	Within 2 h before dosing
Week 5	Day 29±3	Pre-dose	Pre-dose	Within 2 h before dosing
Week 9	Day 57±3	Pre-dose	Pre-dose	Within 2 h before dosing
Week 11	Day 71±3(last dose)	Pre-dose	Pre-dose	Within 2 h before dosing
Week 11	Day 77	+144 h (post-last dose)	+6 day (post-last dose)	+/-2 days
Week 13	Day 85	+336 h (post-last dose)	+14 day (post-last dose)	+/-4 days
Week 17	Day 113	+ 1008 h (post-last dose)	+42 day (post-last dose)	+/-7 days
Week 25	Day 169	+ 2352 h (Post-last dose)	+98 day (Post-last dose)	+/-7 days

Note: For subjects discontinued from IMP or withdraw from study, no additional PK sampling except for EOT and EOS visits (if possible) is required after IMP discontinuation.

Version 6.0 19 of 138 April 11,2024

2 Introduction

HMI-115 is a highly specific human monoclonal antibody that will be investigated for safety and efficacy in pre-menopausal women with moderate to severe endometriosis associated pain.

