4.1 Overall Design

This is a Phase 2, multicenter, double-blind, placebo-controlled, randomized study to assess the safety and efficacy of HMI-115 subcutaneously administered monoclonal antibody versus placebo in pre-menopausal women with moderate to severe endometriosis-associated pain. The planned study regions include China, the United States of America (USA) and European countries.

The study will comprise of three periods (refer to Figure 1-1):

- 1. **Screening Period** of up to 75 days prior to first dose
 - Screening Visit 1
 - Screening Visit 2 (at least 35 days before V3 to ensure at least 5 weeks baseline pain score obtained before randomization)
- 2. **Treatment Period** (12 weeks). Subjects will be given subcutaneous (s.c.) injections Q2W in the study.

3. Follow-up Period of 12 weeks

Eligible subjects will be randomized into four arms: placebo, 60 mg, 120 mg, and 240 mg HMI-115 in a 1:1:1:1 ratio with 38 subjects/arm.

Blood samples will be collected to determine PK profile from Day 1 to Day 169. A full PK sampling strategy will be followed for a subgroup of 10 subjects per arm (refer to Table1-2). Sparse sampling will be obtained from the rest of the subjects (refer to Table1-3). Plasma concentrations of HMI-115 will be determined using a validated enzyme-linked immunosorbent assay (ELISA) method. PK parameters will be assessed as described in Section 9.4.9.

An e-Diary will be dispensed, and training will be provided to subjects at the Visit 2 on how to record endometriosis-associated pain, uterine bleeding, and rescue medication use for endometriosis-associated pain on a daily basis. Study-related examinations, laboratory assessments and pregnancy testing will be performed according to the SoA throughout the study (refer to Table 1-1).

Note: Environmental sanitization procedures will be implemented in the study site and where study procedures are conducted. The study design and associated safety measures are deemed appropriate for conduct during COVID-19 pandemic.

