5.1 Inclusion Criteria

Subjects are eligible to be included in the study only if all of the following criteria apply:

- 1. Pre-menopausal female subjects, between 18 and 49 years of age, inclusive, at the time of signing informed consent.
- 2. Subject must have a clinical diagnosis of endometriosis (laparoscopy or laparotomy) as documented by medical records within 10 years before screening.
- 3. Subject must have a Composite Pelvic Signs and Symptoms Score (CPSSS, refer to Section 8.11 and 10.9) total score of ≥ 6 at screening with a score of at least 2 for DYS and at least 2 for NMPP.
- 4. Subject must have reported at Baseline at least 2 days of "moderate" or "severe" pain for DYS and NMPP, with NRS score of at least 4 (where 0 represents absence of pain and 10 indicates unbearable pain, refer to Section 8.1.3 and 10.6).
- 5. Mammography or contrast-enhanced breast MRI performed within the last 12 months prior to randomization without clinically significant abnormal findings in subjects aged 40 and over only (subject with BI-RADS Classification 1 3 is eligible for randomization).
- 6. Subject must have at least two consecutive regular menstrual cycle (i.e. 21 to 35 days in duration) prior to Day 1.
- 7. Subject agrees to use required (nonhormonal) birth control methods during the entire length of participation in the study (refer to Section 10.4) and agrees to avoid pregnancy from signing the informed consent until 3 months after the last dose.
- 8. Subject must agree to use only those rescue analgesics (i.e. not prophylaxis) permitted by the protocol during the Screening, Treatment and Posttreatment follow-up Periods for her endometriosis-associated pain. (refer to Section 6.5.1).

Version 6.0 33 of 138 April 11, 2024

- 9. In the Investigator's opinion, subject is able to understand the nature of the study and any risk involved in participation in this study and is willing to cooperate and comply with the protocol restrictions and requirements, including transvaginal ultrasound (TVU).
- 10. Subject agrees not to participate in another interventional study while participating in the present study.
- 11. Subject who is willing to limit alcohol consumption during the study to no more than approximately one alcoholic drink or equivalent [beer (354 mL/12 ounces), wine (118 mL/4 ounces), or distilled spirits (29.5 mL/1 ounce)] per day.

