9.4.4 Primary Efficacy Endpoints

The primary efficacy endpoint is the mean change of DYS measured by NRS from Baseline to Week 12.

Measurement of Baseline: The baseline measurements will be derived from the last *complete* menstruation cycle during the Screening Period prior to Day 1.It will be designated as the baseline menstrual cycle and is defined as the interval from the first day of the menstruation to the day before the first day of the next menstruation.

Measurement of Week 12: Because the Week 12 (EOT) visit may or may not occur during menstruation, the measurement of Week 12 will be defined by the following 2 approaches, depending on the scenarios. The objective of these approaches is to capture a complete menstrual cycle and designate it as the EOT menstrual cycle.

- If EOT visit occurs during menstruation, the *EOT menstrual cycle* is defined as the interval that begins from the first day after the end of the previous menstruation to the last day of the menstruation during which the EOT visit occurred. It is expected that the end of this menstruation may be days after the EOT visit.
- If EOT visit occurs outside of a menstruation period, the closest menstruation period to the EOT visit will be identified. This menstrual period may be before or after the EOT visit. In either case, the *EOT menstrual cycle* will begin at the end of the menstruation

Version 6.0 64 of 138 April 11, 2024

period *immediately before* the closest menstruation period to the last day of the closest menstruation period.

The mean change will be summarized for each treatment group with point estimate and 95% CI and will be compared for each HMI-115 treatment group to the placebo group using analysis of covariance models (ANCOVA) with treatment, the randomization stratification factor of region as the fixed effects and baseline DYS as covariate. In addition, a mixed-effect model repeated measures (MMRM) method with treatment, the randomization stratification factor of region, and visit as the main effects, and treatment-by-visit interaction will be used as a sensitivity analysis.

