7.2 Primary Efficacy Endpoint

7.2.1 Definition of Endpoint

[figure not shown]
The primary efficacy endpoint is the mean change of DYS measured by NRS from Baseline to Week 12 measurement. The NRS for overall endometriosis-associated pain ranges from 0 (no pain) to 10 (severe pain). Higher scores mean a worse outcome.

- The Baseline measurement will be derived from the last complete menstruation cycle (menstruation period should be ≥ 2 days) during the Screening Period prior to Day 1. It will be designated as the baseline menstrual cycle and is defined as following:

[figure not shown]
- If the first administration of IMP occurs within the menstruation but not the last day of the menstruation, the baseline menstrual cycle is defined as the interval that first day of the previous menstruation to the day before the menstruation during which the first administration of IMP occurs.

- If the first administration of IMP occurs on the last day of the menstruation, the baseline menstrual cycle is defined as the interval that begins from the first day after the end of the previous menstruation to the first dosing day.

[figure not shown]

- If the first administration of IMP does not occur during the menstruation, the baseline menstrual cycle is defined as the last menstruation period before the first dose plus the non-menstrual period prior to the last menstruation.

[figure not shown]

- The Week 6 measurement will be from a complete menstrual cycle (menstruation period should be ≥ 2 days) prior to Week 7.

[figure not shown]
- If Week 7 visit occurs during menstruation, the menstrual cycle is defined as the interval that begins from the first day after the end of the previous menstruation to the last day of the menstruation during Week 7 visit occurred. It is expected that the end of this menstruation may be days after the Week 7 visit.

- If Week 7 visit occurs outside of a menstruation period, the closest menstruation period to Week 7 visit will be identified. This menstrual period may be before or after the Week 7 visit. In either case, the menstrual cycle will begin at the end of the menstruation period immediately before the closest menstruation period to the last day of the closest menstruation period.

[figure not shown]

Or

[figure not shown]

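### The 35-day minimum from Visit 2 to Visit 3 does not guarantee the complete diary-recorded menstrual cycle that the primary baseline needs

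*Protocol*

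**What the plan says.** Protocol 4.1 places Visit 2 "at least 35 days before V3 to ensure at least 5 weeks baseline pain score obtained before randomization", and footnote 2 of the Schedule of Activities repeats the minimum: "The time interval between Visit 2 and Visit 3 will at least cover a 35-day baseline period". Footnote 23 starts the daily e-Diary at Visit 2. Footnote 3 adds that "Day 1 should start from the menses cycle days 1 to 5". Inclusion criterion 6 reads: "Subject must have at least two consecutive regular menstrual cycle (i.e. 21 to 35 days in duration) prior to Day 1".

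Protocol 9.4.4 takes baseline from the last complete cycle in screening, "defined as the interval from the first day of the menstruation to the day before the first day of the next menstruation". SAP 7.2.1 agrees that baseline is "derived from the last complete menstruation cycle (menstruation period should be ≥ 2 days) during the Screening Period", and then gives three cases:

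- Dosing within menses but before its last day: the window is the previous menstruation up to the day before the current one, as in the protocol.
- Dosing on the last day of menses: the current menstruation is used.
- Dosing outside menses: the latest menstruation before the dose is used.

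Footnote 16 says that sex-hormone samples, which are scheduled at Visit 2 among others, "will be collected at the menses cycle days 1 to 5, and subjects should not take any opioids 2 days prior". Footnote 17 allows a separate day for that sample. Its marker appears at Visits 5, 7, 9 and 10 but not at Visit 2.

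**The concern.** The visit schedule secures five weeks of scores, while the endpoint needs a whole cycle counted from the first day of a menstruation. These are different requirements. No section asks for a complete recorded cycle before randomization. A site that follows the schedule exactly can therefore dose a woman whose diary began after her baseline menstruation had started.

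That woman has either no complete baseline cycle or, under the SAP's rule of averaging non-missing days, a dysmenorrhea mean over her later menstrual days only. Her end-of-treatment score covers a whole menstruation, so the two halves of the change score are not like for like. The baseline score is also the ANCOVA covariate, and the same cycle is the comparator for the 15% rescue-use rule in SAP 7.2.2.

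**Working it through.** **Inputs.** Minimum interval 35 days (5 weeks x 7 = 35, which reproduces the stated purpose). Cycle length L = 21 to 35 (inclusion 6). Cycle day of first dose d = 1 to 5 (footnote 3). Cycle day of Visit 2 c = 1 to 5, as footnote 16 implies. First diary day is Visit 2, or the day before it if the first entry is credited with the previous calendar day (Protocol 8.1.3). The length of menses, m, is not given; I assume 5 days and also show 6 or more.

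**Step 1: how far back the baseline menstruation starts.** It begins L + d - 1 days before Visit 3. The maximum is 35 + 5 - 1 = 39 days, against 35 guaranteed, so up to 4 days can be missed. At L = 31 the maximum is 31 + 5 - 1 = 35, so nothing is lost. L = 32 with d = 5 gives 36, the first shortfall. If the first entry covers the day before Visit 2, the range becomes 33 to 35 days and the maximum loss is 3.

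**Step 2: which visit pairs are affected.** With Visit 3 at the next menses, the interval is L + d - c, which must be at least 35. The diary misses c - 1 menstrual days. Under the SAP the score is affected only if c > 1 and d < m.

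| L | Permitted pairs | Affected, m = 5 | Days lost, m = 5 | Affected, m = 5, first entry covers the day before Visit 2 | Affected, m of 6 or more, or protocol definition |
|---|---|---|---|---|---|
| 32 | 3 | 0 | none | 0 | 1 |
| 33 | 6 | 1 | 1 | 0 | 3 |
| 34 | 10 | 3 | 1-2 | 1 | 6 |
| 35 | 15 | 6 | 1-3 | 3 | 10 |

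The last column also covers the protocol definition, because Protocol 9.4.4 lacks the SAP's second and third cases. These are counts of permitted combinations, not probabilities.

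**Step 3: if Visit 2 could fall on any cycle day**, equally often, with Visit 3 on the first permitted day, the affected shares with m = 5 are 0/32, 1/33 (3%), 2/34 (6%) and 3/35 (9%) for L = 32 to 35.

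**Step 4: effect on one woman's score (assumed values).** Daily scores of 8, 8, 5, 5, 5 average 31/5 = 6.2. Losing the first day gives 23/4 = 5.75; losing two gives 15/3 = 5.0.

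**Step 5: effect on the rescue comparator (assumed values).** Two pills on each of 5 menstrual days in a 35-day cycle average 10/35 = 0.286 per day. With one day unrecorded the baseline is 8/34 = 0.235; with two, 6/33 = 0.182. Unchanged use at end of treatment then looks like a rise of 0.286/0.235 - 1, about 21%, or 0.286/0.182 - 1, about 57%. Both cross the 15% threshold, and any improvement would be set to zero.

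**Step 6: would an existing check catch it?** Since L is at most 35, an interval of 35 or more requires c no greater than d. With d at most m - 1, at least m - (m - 2) = 2 menstrual days remain if the two menstruations are equally long. Neither the SAP's 2-day minimum nor the 2-day pain criterion (inclusion 4) need detect the truncation.

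**The case against.** Thirty-five days is a minimum, and a longer interval can avoid the problem. The SAP's second and third cases protect women dosed on or after the last day of menses, and diary recall may recover one more day. All of this stands and is reflected in the counts, but none of it supplies the guarantee.

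Placing Visit 2 on cycle days 1 to 5 is an inference from the hormone sample and the missing footnote 17 marker. That table row does not read cleanly, so the marker should be confirmed. Step 3 shows that the gap remains, but smaller, without the inference.

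It can also be said that SAP 7.2.2 imputes any missing change score, so an incomplete cycle need not mean a lost subject. That is fair. The SAP does not say, however, whether an incomplete baseline cycle is averaged or treated as missing.

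A reader might infer a biased treatment comparison. The documents do not support that: truncation precedes randomization and is expected equally in all arms. Nor should one woman's shift in Step 4 be set against the 1.4-point between-group difference. It is not an arm mean, and Protocol 9.2 says that the sample size is not based on power for a comparison with placebo.

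A reader might also infer that a woman with 5-day menses and Visit 2 on cycle day 5 is left with one recorded menstrual day. She can reach 35 days at the next menses only with L = 35 and d = 5. That is the last day of a 5-day menses, so the SAP uses the current menstruation.

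**Conclusion.** The point holds as a gap between the visit schedule and the endpoint definition. A fixed 35 days does not ensure a complete recorded cycle when cycles last 32 to 35 days (33 to 35 if the first entry covers the day before Visit 2). With 5-day menses under the SAP, cycles of 33 to 35 days can lose 1 to 3 menstrual days. With menses of 6 days or more, cycles of 32 to 35 days can lose 1 to 4.

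The harm is to the baseline score, the within-group change and the rescue comparator in a minority of unknown size. The documents give no distribution of cycle length, so the share of the 152 subjects cannot be computed. This is a cheap improvement, not a threat to the randomized comparison.

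**What to change.** In footnote 2 of the Schedule of Activities and in Protocol 1.1 and 4.1, require at least 35 days and one complete e-Diary cycle, from the first day of a menstruation to the day before the next, before Visit 3. Check this at Visit 3. Confirm whether the separate-day hormone option in footnote 17 applies to Visit 2; if it does not, attach it, so that Visit 2 and the diary can start before menses. For women already dosed, the SAP should state how an incomplete baseline cycle is handled.

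The cost is an eligibility check and, for some women with long cycles, up to about one extra cycle of screening. For example, with L = 35 and Visit 1 on cycle day 2, the next menses starts 34 days later and dosing falls 34 + 35 = 69 to 73 days after Visit 1, within the 75-day limit.

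The two changes belong together. If Visit 2 stays tied to menses and falls on cycle day 2, 14 days after Visit 1, a complete cycle would take 14 + 34 + 35 = 83 days, beyond the limit.

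A fixed 39-day minimum would also close the gap, but it delays women who are not at risk. With L = 31 and Visit 2 on cycle day 1, Visit 3 would move from day 35 to day 62.
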